#### J. Potential Conflict of Interest

The investigators have no financial, material or proprietary interest in this study.

# K. Location of the Study

This study will be conducted primarily out of the Division of Infectious Diseases outpatient HIV clinic with cooperation of the division. The Division of Addiction Medicine will also be involved in this study and the subjects in the treatment arm will receive their treatment intervention in the division's outpatient research clinic with the cooperation of the division.

# The Drug Abuse Screening Test (DAST)

For each question below, please circle either a Yes or No

1.	Have you used drugs other than those required for medical reasons?	Yes or No
2.	Have you abused prescription drugs?	Yes or No
3.	Do you abuse more than one drug at a time?	Yes or No
4.	Can you get through the week without using drugs (other than those required for medical reasons)?	Yes or No
5.	Are you always able to stop using drugs when you want to?	Yes or No
6.	Do you abuse drugs on a continuous basis?	Yes or No
7.	Do you try to limit your drug use to certain situations?	Yes or No
8.	Have you had "blackouts" or "flashbacks" as a result of drug use?	Yes or No
9.	Do you ever feel bad about your drug abuse?	Yes or No
10.	Does your spouse (or parents) ever complain about your involvement with drugs?	Yes or No
11.	Do your friends or relatives know or suspect you abuse drugs?	Yes or No
12.	Has drug abuse ever created problems between you and your spouse?	Yes or No
13.	Has any family member ever sought help for problems related to drug use?	Yes or No
14.	Have you ever lost friends because of your use of drugs?	Yes or No
15.	Have you ever neglected your family or missed work because of your use of drugs?	Yes or No
16.	Have you ever been in trouble at work because of drug abuse?	Yes or No
17.	Have you ever lost a job because of drug abuse?	Yes or No
18.	Have you gotten into fights when under the influence of drugs?	Yes or No
19.	Have you ever been arrested because of unusual behavior while under the influence of drugs?	Yes or No
20.	Have you ever been arrested for driving while under the influence of drugs?	Yes or No
21.	Have you engaged in illegal activities in order to obtain drugs?	Yes or No
22.	Have you been arrested for possession of dangerous drugs?	Yes or No
23.	Have you ever experienced withdrawal symptoms as a result of heavy drug intake?	Yes or No
24.	Have you had medical problems as a result of your drug use (e.g., memory loss, hepatitis, convulsions, bleeding, etc.)?	Yes or No
25.	Have you ever gone to anyone for help for a drug problem?	Yes or No
26.	Have you ever been in a hospital for medical problems related to drug use?	Yes or No
27.	Have you ever been involved in a treatment program specifically related to drug care?	Yes or No
28.	Have you been treated as an out-patient for problems related to drug use?	Yes or No

The score is equal to the number of questions you answered **Yes** A score of 5 or less points indicates a Normal Score. A score of 6 or more points indicates a Drug Problem.

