# G. Study Subjects

In order to be included in this study, the patient must meet the following inclusion criteria:

- 1) Have documentation of HIV-1 positive status
- 2) Have a positive score on the Drug Abuse Screening Test (DAST)
- 3) Use cocaine regularly and more often than any other drug or alcohol
- 4) Express an interest in stopping their cocaine use
- 5) Must not be currently taking antiretroviral therapy
- 6) Have a viral load >55,000 copies/ml and a CD4 count < 200; thereby placing the subject in a category that should definitely receive therapy according to national guidelines [8b]. Treatment at higher CD4 loads and lower viral loads has still not been shown to affect clinical outcomes of time to disease progression and given the likelihood of non-adherence in drug-abusing populations is higher than in the general population, it may be unethical to start people on HAART when there are uncertain recommendations at present.

If a subject meets any of the following exclusion criteria, they will not be allowed to participate in the study:

- 1) On any form of antiretroviral therapy within the 4 months prior to the study
- 2) Exhibiting signs of physical dependence on any drug other than cocaine
- 3) Living in a facility where medicines are dispensed for them
- 4) Unable to give informed consent

Subject participation will not be limited on the basis of gender or race. Based on population of the community in which the study is to take place, Caucasian, Latino and African-American subjects will be primarily recruited. It is likely that slightly more men will be included in men as there are a larger proportion of male drug abusers in the general population.

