- T F 30.\* I am sometimes irritated by people who ask favors of me.
- T F 31. I have never felt that I was punished without cause.
- T F 32.\* I sometimes think when people have a misfortune, they only got what they deserved.
- T F 33. I have never deliberately said something that hurt someone's feelings.

**Note:** Items marked with an asterisk are keyed negatively. To compute the social desirability score, sum the number of T responses to non-asterisked questions and the number of F responses to asterisked questions.

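### The DAST scoring line counts items 4 and 5 in the wrong direction, shifting the entry score by up to 2 points and misclassifying some patients near the cut-off of 6

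*Protocol*

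**What the plan says.** The Protocol's appendix prints the 28-item DAST with a scoring line beneath it. The line reads "The score is equal to the number of questions you answered" Yes. Two bands follow: "A score of 5 or less points indicates a Normal Score", and "A score of 6 or more points indicates a Drug Problem". No item is named as an exception.

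Three items matter here:

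- Item 4: "Can you get through the week without using drugs (other than those required for medical reasons".
- Item 5: "Are you always able to stop using drugs when you want to".
- Item 7: "Do you try to limit your drug use to certain situations".

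The score decides entry. Section G, inclusion criterion 2, requires the patient to "Have a positive score on the Drug Abuse Screening Test (DAST". Section H applies the test to every patient who presents for HIV care and makes a positive result a condition of recruitment. Section F supports the cut-off of 6 positive responses with an overall accuracy of 85% against a diagnostic interview.

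The other scale in the appendix, the Marlowe-Crowne, does give reverse keying: "Items marked with an asterisk are keyed negatively".

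**The concern.** A count of Yes answers measures drug problems only if Yes points towards a problem on every item. On items 4 and 5 it points the other way. A patient who says he can do without drugs for a week, or can always stop, gains a problem point. A patient who says he cannot gains nothing. The scoring line therefore contradicts the wording of two items that it scores.

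What is at stake is the composition of the trial population. A patient who reports loss of control faces a stricter effective threshold than one who reports control, which is the reverse of what the screen is for. Some intended patients near the cut-off may be turned away and some others admitted. The accuracy figure that justifies the cut-off may also not carry over to a score keyed in this way.

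**Working it through.** No sample size, power or significance level depends on this point, so the check is an enumeration of scores.

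**Inputs**

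- 28 items; 1 point per Yes; positive at 6 or more, normal at 5 or less (appendix, DAST).
- Items 4 and 5: Yes is the no-problem answer (item wording).
- The other 26 items, item 7 included, are taken as printed, with Yes as the problem answer.

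**Formulas**

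Let o be the number of Yes answers on the other 26 items (0 to 26), and y the number on items 4 and 5 (0, 1 or 2).

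- Printed score: P = o + y
- Score with items 4 and 5 reversed: C = o + (2 − y)
- Error: P − C = 2y − 2

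**Range of the score**

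- Every answer in the no-problem direction (o = 0, y = 2): P = 2, where C = 0.
- Every answer in the problem direction (o = 26, y = 0): P = 26, where C = 28.

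**Who changes side at the cut-off of 6**

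| Answers to items 4 and 5 | P − C | Values of o at which eligibility changes | Result |
|---|---|---|---|
| No to both (y = 0) | −2 | 4, 5 | P = 4 or 5 (normal), C = 6 or 7 (drug problem): wrongly excluded |
| One Yes, one No (y = 1) | 0 | none | errors cancel |
| Yes to both (y = 2) | +2 | 4, 5 | P = 6 or 7 (drug problem), C = 4 or 5 (normal): wrongly qualifies |

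Put another way, a patient who answers No to both items needs a correctly keyed score of 6 + 2 = 8 to qualify, and one who answers Yes to both qualifies at 6 − 2 = 4.

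**Sensitivity to item 7, as an assumption only**

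If item 7 were also reverse-keyed, 25 other items remain and P − C = 2y − 3, with y from 0 to 3. The largest error is 3 points. Patients who answer all three items alike change side at o = 3, 4 or 5; those with mixed answers change side only at o = 4. The item's wording does not settle whether this case applies, since trying to confine drug use to certain situations can signal either control or difficulty.

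**The case against.** The strongest reply is that the effect is narrow. Only two of 28 items are shown to run backwards, and the total still rises with drug problems. Opposite answers to items 4 and 5 cancel, and outside o = 4 or 5 nothing changes. This stands and limits the point. A reader might infer that eligibility as a whole is scored in the wrong direction; the documents do not support that.

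A reader might also put the error at 3 points, so that a true score of 8 falls to 5 or a true 3 rises to 6. Both examples need item 7 to be reversed. With items 4 and 5 alone, a true 8 falls to 6 and still qualifies, and a true 3 rises to 5 and still does not.

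Next, other criteria act as a filter. Section G separately requires regular cocaine use, more frequent than any other drug or alcohol (criterion 3), and an interest in stopping (criterion 4). Section H asks that the patient want help. These limit wrongful inclusion, so an inference that milder users enter and dilute the effect of therapy is speculative. They do nothing for wrongful exclusion: a regular cocaine user who cannot stop and scores 4 or 5 instead of 6 or 7 fails criterion 2 regardless.

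Finally, the DAST is applied before randomisation, identically for both arms, and is neither an outcome nor a listed covariate. A reader who infers bias in the treatment comparison would be wrong.

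Two supporting arguments carry little weight. Reverse keying on the Marlowe-Crowne scale does not prove an omission on the DAST; the item wording has to carry the point, and it does. Section F does not say how a positive response was keyed in the accuracy study, so the remark on the 85% is a caution, not a demonstrated conflict.

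**Conclusion.** The point holds in a limited form. The printed rule is wrong on its face for items 4 and 5, in a score that decides an inclusion criterion. The provable error is at most 2 points. It changes eligibility, in either direction, only for patients with exactly 4 or 5 Yes answers on the other 26 items who answer items 4 and 5 alike.

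This rests on reading Yes to items 4 and 5 as a statement of control, which their wording makes plain, and on taking the other 26 items as printed. The documents give no score distribution, so the number of patients affected is unknown and may be small. The consequence is for who is enrolled and for whether the quoted accuracy applies. Severity is moderate: a certain error in an entry criterion that is easily corrected, but not a threat to the validity of the comparison between arms.

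**What to change.** Reword the scoring line in the appendix: score 1 for each Yes, except on items 4 and 5, where No scores 1. Check item 7 against the instrument's published key and add it to the exception only if the key says so. Keep the cut-off of 6. Confirm from the source cited in Section F that the 85% accuracy refers to the score keyed in this way, or qualify the statement.

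Re-score anyone already screened from their item-level answers. The cost is one line in the appendix and on the scoring sheet, plus that re-scoring. Sample size, visits and analyses are unchanged.

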#### Marlowe-Crowne Social Desirability Scale

Listed below are a number of statements concerning personal attitudes and traits. Read each item and decide whether the statement is true or false as it pertains to you.

- T F 1. Before I vote, I thoroughly investigate the qualifications of all of the candidates.
- **T F** 2. I never hesitate to go out of my way to help someone in trouble.
- T F 3.\* It is sometimes hard for me to go on with my work if I am not encouraged.
- T F 4. I have never intensely disliked anyone.
- T F 5.\* On occasion, I have had doubts about my ability to succeed in life.
- **T F** 6.\* I sometimes feel resentful when I don't get my way.
- T F 7. I am always careful about my manner of dress.
- T F 8. My table manners at home are as good as when I eat out in a restaurant.
- T F 9.\* If I could get into a movie without paying and be sure I was not seen, I would probably do it.
- **T F** 10.\* On a few occasions, I have given up doing something because I thought too little of my ability.
- **T F** 11.\* I like to gossip at times.
- T F 12.\* There have been times when I felt like rebelling against people in authority even though I knew they were right.
- T F 13. No matter who I'm talking to, I'm always a good listener.
- **T F** 14.\* I can remember "playing sick" to get out of something.
- T F 15.\* There have been occasions when I took advantage of someone.
- T F 16. I'm always willing to admit it when I make a mistake.
- T F 17. I always try to practice what I preach.
- T F 18. I don't find it particularly difficult to get along with loudmouthed, obnoxious people.
- **T F** 19.\* I sometimes try to get even rather than forgive and forget.
- T F 20. When I don't know something, I don't mind admitting it.
- T F 21. I am always courteous, even to people who are disagreeable.
- T F 22.\* At times I have really insisted on having things done my own way.
- T F 23.\* There have been occasions when I felt like smashing things.
- T F 24. I would never think of letting someone else be punished for my wrongdoings.
- **T F** 25. I never resent being asked to return a favor.
- T F 26. I have never been irked when people express ideas very different from my own.
- T F 27. I never make a long trip without checking the safety of my car.
- T F 28.\* There have been times when I was quite jealous of the good fortune of others.
- T F 29. I have almost never felt the urge to tell someone off.
- T F 30.\* I am sometimes irritated by people who ask favors of me.
- T F 31. I have never felt that I was punished without cause.
- T F 32.\* I sometimes think when people have a misfortune, they only got what they deserved.
- T F 33. I have never deliberately said something that hurt someone's feelings.

**Note:** Items marked with an asterisk are keyed negatively. To compute the social desirability score, sum the number of T responses to non-asterisked questions and the number of F responses to asterisked questions.

# Three Day Adherence Questionaire (Part A)

**Note**: The chart below should be customized to the client's antiretrovirals. Steps 1-3 should be generated interactively with the client, and should be an accurate representation of the client's current drug regimen. Please use prompts or visual aids if necessary to complete the table with the client. Please fill in"dk" for don't know if patient is unable to fill in an area of the chart.

Step 1 Names of antiretroviral drugs	Step 2 # pills taken at each dose	Step 3 # times dose is taken per day	Step 4 # doses missed Yesterday	Step 5 # doses missed 2 days ago	Step 6 # doses missed 3 days ago
1)					
2)					
3)					
4)					
5)					

If there were no reported missed doses in the chart above, please ask the following questions:

- 6. When was the last time you skipped any of your medications?
  - a. never skip medications
  - b. more than two weeks ago
  - c. 1-2 weeks ago
  - d. within the past week

# Three Day Adherence Questionnaire (Part B)

Check one response for each of the following questions regarding reasons why you missed taking your medication: N=Never, R=Rarely, S=Sometimes, O=Often.

a)	Taking pills didn't fit in with your daily routine?	NRSO
b)	Simply forgot?	NRSO
c)	Too hard to take so many pills according to a schedule?	NRSO
d)	Wanted to avoid side effects?	NRSO
e)	Felt like the drug was toxic/harmful?	NRSO
f)	Did not want others to notice you taking medication?	NRSO
g)	Feel asleep/slept through dose time?	NRSO
h)	Felt sick or ill?	NRSO
i)	Felt depressed/overwhelmed?	NRSO
j)	Ran out of pills?	NRSO
k)	Felt good?	NRSO
l)	Didn't understand regimen?	NRSO
m)	You knew what was best for you?	NRSO
n)	Didn't fit with meals/didn't have water?	NRSO
0)	Didn't feel like taking pills?	NRSO
p)	Were drunk or high?	NRSO
